Immune-mediated myositis, Grade 2	
Withhold atezolizumab/tiragolumab/RO7247669 for up to 12 weeks after event onset ^a and contact the Medical Monitor.Refer patient to rheumatologist or neurologist.Initiate treatment as per institutional guidelines.Consider treatment with corticosteroids equivalent to 1–2 mg/kg/day IV methylprednisolone and convert to 1–2 mg/kg/day oral prednisone or equivalent upon improvement.If corticosteroids are initiated and event does not improve within 48 hours after initiating corticosteroids, consider adding an immunosuppressive agent.If event resolves to Grade 1 or better, resume atezolizumab/tiragolumab/RO7247669. ^bIf event does not resolve to Grade 1 or better while withholding atezolizumab/tiragolumab/RO7247669, permanently discontinue atezolizumab/tiragolumab/RO7247669 and contact the Medical Monitor. ^c

^a For Cohort 2, RO7247669 and tiragolumab may be withheld for a longer period of time (i.e., >12 weeks after event onset) to allow for corticosteroids (if initiated) to be reduced to the equivalent of \leq 10 mg/day oral prednisone. The acceptable length of the extended period of time must be based on the investigator's benefit–risk assessment and in alignment with the protocol requirements for the duration of treatment and documented by the investigator. The Medical Monitor is available to advise as needed.

^b If corticosteroids have been initiated, they must be tapered over \geq 1 month to the equivalent of \leq 10 mg/day oral prednisone before atezolizumab/tiragolumab/RO7247669 can be resumed.

^c If a study drug warrants permanent discontinuation, there should be no re-challenge of the drug. For combination regimens, both study drugs should be discontinued.

Appendix 9: Guidelines for Management of Atezolizumab-, Tiragolumab-, and/or RO7247669-Specific Adverse Events

Table A9-14 Management Guidelines for Immune-Mediated Myositis (cont.)

Event	Management
Immune-mediated myositis, Grade 3	
Withhold atezolizumab/tiragolumab/RO7247669 for up to 12 weeks after event onset^a and contact the Medical Monitor.Refer patient to rheumatologist or neurologist.Initiate treatment as per institutional guidelines.Respiratory support may be required in more severe cases.Initiate treatment with corticosteroids equivalent to 1–2 mg/kg/day IV methylprednisolone, or higher-dose bolus if patient is severely compromised (e.g., cardiac or respiratory symptoms, dysphagia, or weakness that severely limits mobility); convert to 1–2 mg/kg/day oral prednisone or equivalent upon improvement.If event does not improve within 48 hours after initiating corticosteroids, consider adding an immunosuppressive agent.If event resolves to Grade 1 or better, resume atezolizumab/tiragolumab/RO7247669.^bIf event does not resolve to Grade 1 or better while withholding atezolizumab/tiragolumab/RO7247669, permanently discontinue atezolizumab/tiragolumab/RO7247669 and contact the Medical Monitor.^cFor recurrent events, treat as a Grade 4 event. Permanently discontinue atezolizumab/tiragolumab/RO7247669 and contact the Medical Monitor.^c

^a For Cohort 2, RO7247669 and tiragolumab may be withheld for a longer period of time (i.e., >12 weeks after event onset) to allow for corticosteroids (if initiated) to be reduced to the equivalent of ≤10 mg/day oral prednisone. The acceptable length of the extended period of time must be based on the investigator's benefit–risk assessment and in alignment with the protocol requirements for the duration of treatment and documented by the investigator. The Medical Monitor is available to advise as needed.

^b If corticosteroids have been initiated, they must be tapered over ≥1 month to the equivalent of ≤10 mg/day oral prednisone before atezolizumab/tiragolumab/RO7247669 can be resumed.

^c If a study drug warrants permanent discontinuation, there should be no re-challenge of the drug. For combination regimens, both study drugs should be discontinued.

Appendix 9: Guidelines for Management of Atezolizumab-, Tiragolumab-, and/or RO7247669-Specific Adverse Events

Table A9-14 Management Guidelines for Immune-Mediated Myositis (cont.)

Event	Management
Immune-mediated myositis, Grade 4	
• Permanently discontinue atezolizumab/tiragolumab/RO7247669 and contact the Medical Monitor.^c• Refer patient to rheumatologist or neurologist.• Initiate treatment as per institutional guidelines. Respiratory support may be required in more severe cases.• Initiate treatment with corticosteroids equivalent to 1–2 mg/kg/day IV methylprednisolone, or higher-dose bolus if patient is severely compromised (e.g., cardiac or respiratory symptoms, dysphagia, or weakness that severely limits mobility); convert to 1–2 mg/kg/day oral prednisone or equivalent upon improvement.• If event does not improve within 48 hours after initiating corticosteroids, consider adding an immunosuppressive agent.• If event resolves to Grade 1 or better, taper corticosteroids over ≥ 1 month.

^a For Cohort 2, RO7247669 and tiragolumab may be withheld for a longer period of time (i.e., > 12 weeks after event onset) to allow for corticosteroids (if initiated) to be reduced to the equivalent of ≤ 10 mg/day oral prednisone. The acceptable length of the extended period of time must be based on the investigator's benefit–risk assessment and in alignment with the protocol requirements for the duration of treatment and documented by the investigator. The Medical Monitor is available to advise as needed.

^b If corticosteroids have been initiated, they must be tapered over ≥ 1 month to the equivalent of ≤ 10 mg/day oral prednisone before atezolizumab/tiragolumab/RO7247669 can be resumed.

^c If a study drug warrants permanent discontinuation, there should be no re-challenge of the drug. For combination regimens, both study drugs should be discontinued.

A9-19 HEMOPHAGOCYTIC LYMPHOHISTIOCYTOSIS AND MACROPHAGE ACTIVATION SYNDROME

Immune-mediated reactions may involve any organ system and lead to hemophagocytic lymphohistiocytosis (HLH) and macrophage activation syndrome (MAS), which are considered to be potential risks for atezolizumab.

Clinical and laboratory features of severe CRS overlap with HLH, and HLH should be considered when CRS presentation is atypical or prolonged.

Appendix 9: Guidelines for Management of Atezolizumab-, Tiragolumab-, and/or RO7247669-Specific Adverse Events

Patients with suspected HLH should be diagnosed according to published criteria by McClain and Eckstein (2014). A patient should be classified as having HLH if five of the following eight criteria are met:

- Fever $\geq 38.5^{\circ}\text{C}$
- Splenomegaly
- Peripheral blood cytopenia consisting of at least two of the following:
 - Hemoglobin $< 90 \text{ g/L}$ (9 g/dL) ($< 100 \text{ g/L}$ [10 g/dL] for infants < 4 weeks old)
 - Platelet count $< 100 \times 10^9/\text{L}$ ($100,000/\mu\text{L}$)
 - ANC $< 1.0 \times 10^9/\text{L}$ ($1000/\mu\text{L}$)
- Fasting triglycerides $> 2.992 \text{ mmol/L}$ (265 mg/dL) and/or fibrinogen $< 1.5 \text{ g/L}$ (150 mg/dL)
- Hemophagocytosis in bone marrow, spleen, lymph node, or liver
- Low or absent natural killer cell activity
- Ferritin $> 500 \text{ mg/L}$ (500 ng/mL)
- Soluble IL-2 receptor (soluble CD25) elevated ≥ 2 standard deviations above age-adjusted laboratory-specific norms

Patients with suspected MAS should be diagnosed according to published criteria for systemic juvenile idiopathic arthritis by Ravelli et al. (2016). A febrile patient should be classified as having MAS if the following criteria are met:

- Ferritin $> 684 \text{ mg/L}$ (684 ng/mL)
- At least two of the following:
 - Platelet count $\leq 181 \times 10^9/\text{L}$ ($181,000/\mu\text{L}$)
 - AST $\geq 48 \text{ U/L}$
 - Triglycerides $> 1.761 \text{ mmol/L}$ (156 mg/dL)
 - Fibrinogen $\leq 3.6 \text{ g/L}$ (360 mg/dL)

Patients with suspected HLH or MAS should be treated according to the guidelines in [Table A9-15](#).

Appendix 9: Guidelines for Management of Atezolizumab-, Tiragolumab-, and/or RO7247669-Specific Adverse Events

Table A9-15 Management Guidelines for Suspected Hemophagocytic Lymphohistiocytosis or Macrophage Activation Syndrome

Event	Management
Suspected HLH or MAS	
• Permanently discontinue atezolizumab/tiragolumab/RO7247669 and contact the Medical Monitor.• Consider patient referral to hematologist.• Initiate supportive care, including intensive care monitoring if indicated per institutional guidelines.• Consider initiation of IV corticosteroids, an immunosuppressive agent, and/or anti-cytokine therapy.• If event does not respond to treatment within 24 hours, contact the Medical Monitor and initiate treatment as appropriate according to published guidelines (La Rosée 2015; Schram and Berliner 2015; La Rosée et al. 2019).• If event resolves to Grade 1 or better, taper corticosteroids over ≥ 1 month.

HLH=hemophagocytic lymphohistiocytosis; MAS=macrophage activation syndrome.

Appendix 9: Guidelines for Management of Atezolizumab-, Tiragolumab-, and/or RO7247669-Specific Adverse Events

A9–20 REFERENCES

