4.1.2.4 Exclusion Criteria for RO7247669-Containing Arms (Cohort 1 and Cohort 2)

Patients who meet any of the following criteria will be excluded from the RO7247669-containing arms:

- Prior treatment with an anti-LAG-3 agent
- History of myocarditis (regardless of etiology)
- Left ventricular ejection fraction (LVEF) $< 50\%$ assessed by either transthoracic echocardiogram (TTE) or multiple-gated acquisition (MUGA) scan (TTE preferred test) within 6 months prior to initiation of study treatment
- Troponin T (TnT) or troponin I (TnI) $>$ institutional ULN

Patients with TnT or TnI levels between > 1 and $< 2 \times$ ULN are eligible if repeat levels within 24 hours are $\leq 1 \times$ ULN. If repeat levels within 24 hours are between > 1 and $< 2 \times$ ULN, patients need to undergo a cardiac evaluation and may be considered for treatment if there are no clinically significant findings.

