Appendix 9: Guidelines for Management of Atezolizumab-, Tiragolumab-, and/or RO7247669-Specific Adverse Events

Patients with signs and symptoms of pericarditis, pericardial effusion, or cardiac tamponade, in the absence of an identified alternate etiology, should be treated according to the guidelines in **Table A9-6**. Withhold treatment with atezolizumab, tiragolumab and/or RO7247669 for Grade 1 pericarditis and conduct a detailed cardiac evaluation to determine the etiology and manage accordingly.

Table A9-6 Management Guidelines for Immune-Mediated Cardiac Events

Event	Management
Immune-mediated myocarditis, Grades 2–4	
Permanently discontinue atezolizumab/tiragolumab/RO7247669 and contact the Medical Monitor.^aRefer patient to cardiologist.
Immune-mediated pericardial disorders, Grades 2–4	
Initiate treatment as per institutional guidelines and consider antiarrhythmic drugs, temporary pacemaker, ECMO, VAD or pericardiocentesis as appropriate.Initiate treatment with corticosteroids equivalent to 1–2 mg/kg/day IV methylprednisolone and convert to 1–2 mg/kg/day oral prednisone or equivalent upon improvement.^{b, c}If event does not improve within 48 hours after initiating corticosteroids, consider adding an immunosuppressive agent.If event resolves to Grade 1 or better, taper corticosteroids over \geq 1 month.

ECMO = extracorporeal membrane oxygenation; VAD = ventricular assist device.

^a If a study drug warrants permanent discontinuation, there should be no re-challenge of the drug. For combination regimens, both study drugs should be discontinued.

^b For Cohort 2, RO7247669 and tiragolumab may be withheld for a longer period of time (i.e., $>$ 12 weeks after event onset) to allow for corticosteroids (if initiated) to be reduced to the equivalent of \leq 10 mg/day oral prednisone. The acceptable length of the extended period of time must be based on the investigator's benefit–risk assessment and in alignment with the protocol requirements for the duration of treatment and documented by the investigator. The Medical Monitor is available to advise as needed.

^c If corticosteroids have been initiated, they must be tapered over \geq 1 month to the equivalent of \leq 10 mg/day oral prednisone before atezolizumab/tiragolumab/RO7247669 can be resumed.

A9-11 INFUSION-RELATED REACTIONS

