A9-16 IMMUNE-MEDIATED MENINGOENCEPHALITIS

Immune-mediated meningoencephalitis should be suspected in any patient presenting with signs or symptoms suggestive of meningitis or encephalitis, including, but not limited to, headache, neck pain, confusion, seizure, motor or sensory dysfunction, and altered or depressed level of consciousness. Encephalopathy from metabolic or electrolyte imbalances needs to be distinguished from potential meningoencephalitis resulting from infection (bacterial, viral, or fungal) or progression of malignancy, or secondary to a paraneoplastic process.

All patients being considered for meningoencephalitis should be urgently evaluated with a CT scan and/or MRI scan of the brain to evaluate for metastasis, inflammation, or edema. If deemed safe by the treating physician, a lumbar puncture should be performed and a neurologist should be consulted.

Patients with signs and symptoms of meningoencephalitis, in the absence of an identified alternate etiology, should be treated according to the guidelines in [Table A9-12](#).

Table A9-12 Management Guidelines for Immune-Mediated Meningoencephalitis

Event	Management
Immune-mediated meningoencephalitis, all grades	
• Permanently discontinue atezolizumab/tiragolumab/RO7247669 and contact the Medical Monitor.^a• Refer patient to neurologist.• Initiate treatment with corticosteroids equivalent to 1–2 mg/kg/day IV methylprednisolone and convert to 1–2 mg/kg/day oral prednisone or equivalent upon improvement.• If event does not improve within 48 hours after initiating corticosteroids, consider adding an immunosuppressive agent.• If event resolves to Grade 1 or better, taper corticosteroids over ≥ 1 month.

^a If a study drug warrants permanent discontinuation, there should be no re-challenge of the drug. For combination regimens, both study drugs should be discontinued.

Appendix 9: Guidelines for Management of Atezolizumab-, Tiragolumab-, and/or RO7247669-Specific Adverse Events

A9-17 RENAL EVENTS

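### Table A9-6 orders permanent discontinuation without re-challenge for Grade 2–4 myocarditis and pericardial disorders, yet its steroid bullet carries footnotes on an extended hold and on resuming study drug

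*Combined protocol and SAP*

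**What the plan says.** Table A9-6, in Section A9-10 of Appendix 9, lists two event labels: "Immune-mediated myocarditis, Grades 2–4" and "Immune-mediated pericardial disorders, Grades 2–4". Its only instruction about study drug is "Permanently discontinue atezolizumab/tiragolumab/RO7247669 and contact the Medical Monitor.^a". Footnote a reads "If a study drug warrants permanent discontinuation, there should be no re-challenge of the drug", and adds that both drugs of a combination are to be stopped.

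The corticosteroid bullet in the same table ends "oral prednisone or equivalent upon improvement.^{b, c", so it carries the markers for two further footnotes:

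- Footnote b begins "For Cohort 2, RO7247669 and tiragolumab may be withheld for a longer period of time". It allows a hold beyond 12 weeks from onset so that steroids can be brought down.
- Footnote c requires a taper over at least 1 month, to no more than 10 "mg/day oral prednisone before atezolizumab/tiragolumab/RO7247669 can be resumed".

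The paragraph directly above the table refers pericardial events to Table A9-6. It then tells sites to withhold study drug for Grade 1 pericarditis while the cause is worked up. That sentence has no footnote marker, and the table has no Grade 1 row.

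**The concern.** A reader who follows footnote a ends treatment for good. A reader who follows the markers on the steroid bullet finds a hold length and a condition for restarting, for the same Grade 2–4 events. Footnote c has no purpose if study drug can never be resumed, so its presence suggests that someone expected a restart in some case. The table does not say which case.

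This is a safety table that sites consult under time pressure, and two sites could handle the same cardiac event differently. There is also a secondary link to trial conduct. An adverse event that requires permanent discontinuation is one of the listed events in the rule that puts enrollment on hold when at least 30% of patients have such an event (Sections 3.1.3 and 3.1.4).

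**Working it through.** The check is mainly textual, because the plan states no figure on this point.

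**1. Trace the markers and compare with similar rows.** Footnote letters differ between tables, so the comparison is by function. Every row below orders permanent discontinuation and also contains a steroid bullet.

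| Row in Appendix 9 | Footnote on the discontinuation bullet | Footnote on the steroid bullet |
|---|---|---|
| A9-6, cardiac, Grades 2–4 | no re-challenge (a) | extended hold in Cohort 2 (b); taper before resuming (c) |
| A9-1, pulmonary, Grade 3 or 4 | no re-challenge; resumption also barred for pneumonitis | none |
| A9-2, hepatic, Grade 3 or 4 | no re-challenge | none |
| A9-3, diarrhea or colitis, Grade 4 | no re-challenge | none |
| A9-5, ocular, Grade 3 or 4 | no re-challenge | none |
| A9-12, meningoencephalitis, all grades | no re-challenge | none |

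The steroid wording in the colitis and meningoencephalitis rows matches that of Table A9-6.

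**2. See where the hold and taper footnotes normally sit.** In the Grade 2 hepatic and Grade 2 ocular rows, the hold footnote is attached to a bullet that withholds drug and the taper footnote to a bullet that resumes it. Table A9-6 has neither kind of bullet.

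**3. Rule out a reprinted footer.** Some continuation pages repeat footnotes that nothing on the page uses; the last page of Table A9-4 is an example. In Table A9-6, by contrast, the markers are placed on a bullet.

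**4. Look for another target.** The only cardiac hold is the Grade 1 pericarditis sentence. If footnotes b and c were meant for it, the markers are on the wrong bullet.

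**5. Size the link to the enrollment hold.** The threshold is 30%. With 6 patients, 0.30 × 6 = 1.8. One patient is 1/6 = 16.7%, below the threshold; two are 2/6 = 33.3%, above it. One patient's classification can therefore decide the hold, but only if the event meets no other listed criterion. An event that is serious and treatment-related counts under either reading. So does a Grade 3 or higher event that has not improved to Grade 2 within 2 weeks and, in Cohort 1, an event that delays surgery by more than 2 weeks. What remains is a non-serious event that is Grade 2, or Grade 3 with improvement inside 2 weeks, and that does not delay surgery beyond the limit. The documents give no frequency for such events.

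**The case against.** The strongest reply is that the operative order is clear. The Grade 2–4 text says to stop permanently and to contact the Medical Monitor, and footnote a repeats the bar. Footnote c is a precondition and gives no permission to restart. A site would have to override an explicit order on the strength of a footnote to a steroid bullet. This is right as far as it goes, and it makes harm less likely. It does not give footnotes b and c anything to govern.

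A reader might infer more than the documents support:

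- **That footnotes b and c can refer only to the barred Grade 2–4 events.** The Grade 1 pericarditis hold is a possible target, although nothing links the footnotes to it.
- **That every Grade 2–4 cardiac event in the study is affected.** The control arm follows local prescribing information (Section A11-5.1.2.2). Footnote b covers Cohort 2 only, and the synopsis says that no Cohort 2 arm is open for enrollment. In Cohort 1 there are two 21-day cycles. Section A9-2 allows a later cycle after a toxicity only if surgery can take place within 2 weeks of its planned date, so a taper of a month or more leaves little room to resume.
- **That the entry exclusion "History of myocarditis (regardless of etiology" in Section 4.1.2.4 is a further contradiction.** It governs entry to the RO7247669 arms and says nothing about managing an event on study.

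The layout also leaves some doubt. The two event labels appear to share one merged management cell, but this cannot be confirmed from the text alone. Read as two rows, the discontinuation order would belong to myocarditis and the b and c markers to pericardial disorders. Pericardial disorders would then have no study-drug instruction at all, so that reading does not remove the problem.

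**Conclusion.** The point holds as an internal inconsistency in a safety table. For the events that Table A9-6 covers, permanent discontinuation without re-challenge stands beside footnotes on a longer hold and on the condition for resuming, with no instruction for those footnotes to govern.

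Its reach is the experimental arms: footnote b for RO7247669 and tiragolumab in Cohort 2, footnote c for all three named drugs. It has no bearing on sample size, efficacy estimates or the planned analyses. The effect on the 30% hold is conditional, as the working shows, and should not be presented as the main consequence. The documents also do not support saying that the protocol permits re-challenge after Grade 2–4 myocarditis; they support only that the table and its footnotes disagree.

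The conclusion assumes that the marker placement in the available text matches the issued protocol. It does not depend on whether the management cell is merged.

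**What to change.** The sponsor's clinical team should reconcile four items together: the Grade 2–4 discontinuation instruction, footnote a, footnotes b and c, and the Grade 1 pericarditis sentence above the table. Table A9-6 should then state which events and grades footnotes b and c apply to, if any, and give one study-drug instruction per event and grade. If they apply to an event that the table does not list, that event needs its own row; if they apply to none, the markers have no place in this table. The choice of rule is clinical and is left to the sponsor.

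The cost is an edit to one table and the adjoining paragraph in Appendix 9, which can go into the next amendment. No data collection or analysis changes.

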- Patients and family caregivers should receive timely and up-to-date information about immunotherapies, their mechanism of action, and the clinical profile of possible immune-related adverse events prior to initiating therapy and throughout treatment and long-term follow-up. There should be a high level of suspicion that new symptoms are treatment related.
- In general, atezolizumab, tiragolumab, and/or RO7247669 therapy should be continued with close monitoring for Grade 1 toxicities, with the exception of some neurologic toxicities.
- Consider holding atezolizumab, tiragolumab, and/or RO7247669 for most Grade 2 toxicities and resume when symptoms and/or laboratory values resolve to Grade 1 or better. Corticosteroids (initial dose of 0.5–1 mg/kg/day of prednisone or equivalent) may be administered.
- For Grade 2 recurrent or persistent (lasting for more than 5 days) events, treat as a Grade 3 event.
- Hold atezolizumab, tiragolumab, and/or RO7247669 for Grade 3 toxicities and initiate treatment with high-dose corticosteroids (1–2 mg/kg/day prednisone or equivalent). Corticosteroids should be tapered over 1 month to 10 mg/day oral prednisone or equivalent, before atezolizumab, tiragolumab, and/or RO7247669 can be resumed. If symptoms do not improve within 48 to 72 hours of high-dose corticosteroid use, other immunosuppressants may be offered for some toxicities.
- In general, Grade 4 toxicities warrant permanent discontinuation of atezolizumab, tiragolumab, and/or RO7247669 treatment, with the exception of endocrinopathies that are controlled by hormone-replacement therapy.
- The investigator should consider the benefit–risk balance for a given patient prior to further administration of atezolizumab, tiragolumab, and/or RO7247669. Resumption of atezolizumab, tiragolumab, and/or RO7247669 may be considered in patients who are deriving benefit and have fully recovered from the immune-mediated event. The decision to re-challenge patients with atezolizumab, tiragolumab, and/or RO7247669 should be based on the investigator’s assessment of the benefits and risks and documented by the investigator. The Medical Monitor is available to advise as needed.

A9-1 DOSE MODIFICATIONS

There will be no dose modifications for atezolizumab, tiragolumab, or RO7247669 in this study.

Appendix 9: Guidelines for Management of Atezolizumab-, Tiragolumab-, and/or RO7247669-Specific Adverse Events

A9–2 TREATMENT INTERRUPTION

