Treatment with atezolizumab, tiragolumab, or RO7247669 may be temporarily suspended in patients experiencing toxicity considered to be related to study treatment. If corticosteroids are initiated for treatment of the toxicity, they must be tapered over ≥ 1 month to the equivalent of ≤ 10 mg/day oral prednisone before atezolizumab, tiragolumab, and/or RO7247669 can be resumed.

For Cohort 1, treatment with atezolizumab, tiragolumab, and/or RO7247669 should not be interrupted unless a patient experiences toxicity. If toxicity meets criteria for interrupting/withholding study drug(s), study drug(s) should be interrupted/withheld. After resolution of the toxicity, subsequent treatment cycles should only be considered if the benefit–risk profile is acceptable and if the surgery can be conducted within 2 weeks of the planned date. Otherwise, subsequent treatment cycles should be omitted to allow the patient to proceed directly to surgery without further delay.

For Cohort 2, if RO7247669 and tiragolumab are withheld for 12 weeks or longer due to toxicity, the patient should be discontinued from RO7247669 and tiragolumab. However, RO7247669 and tiragolumab may be withheld for more than 12 weeks to allow for patients to taper off corticosteroids prior to resuming treatment. RO7247669 and tiragolumab may be resumed after being withheld for more than 12 weeks if the patient is likely to derive clinical benefit. RO7247669 and tiragolumab treatment may be suspended for reasons other than toxicity (e.g., surgical procedures) at the discretion of the investigator. The acceptable length of the extended period of time must be based on the investigator's benefit–risk assessment and in alignment with the protocol requirements for the duration of treatment and documented by the investigator. The Medical Monitor is available to advise as needed.

A9–3 PULMONARY EVENTS

Pulmonary events may present as new or worsening cough, chest pain, fever, dyspnea, fatigue, hypoxia, pneumonitis, and pulmonary infiltrates. Patients will be assessed for pulmonary signs and symptoms throughout the study and will also have computed tomography (CT) scans of the chest performed at every tumor assessment.

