Grade 2^a Fever ^b with at least one of the following: 
 Hypotension not requiring vasopressors Hypoxia requiring low-flow oxygen^d by nasal cannula or blowby 	
 Immediately interrupt infusion. Upon symptom resolution, wait for 30 minutes and then restart infusion at half the rate being given at the time of event onset. If symptoms recur, discontinue infusion of this dose. Administer symptomatic treatment.^c For hypotension, administer IV fluid bolus as needed. Monitor cardiopulmonary and other organ function closely (in the ICU, if appropriate). Administer IV fluids as clinically indicated, and manage constitutional symptoms and organ toxicities as per institutional practice. Rule out other inflammatory conditions that can mimic CRS (e.g., sepsis). If no improvement within 24 hours, initiate workup and assess for signs and symptoms of HLH or MAS as described in this appendix. Consider IV corticosteroids (e.g., methylprednisolone 2 mg/kg/day or dexamethasone 10 mg every 6 hours). Consider anti-cytokine therapy.^e Consider hospitalization until complete resolution of symptoms. If no improvement within 24 hours, manage as per Grade 3, that is, hospitalize patient (monitoring in the ICU is recommended), permanently discontinue atezolizumab/tiragolumab/RO7247669, and contact the Medical Monitor. If symptoms resolve to Grade 1 or better for 3 consecutive days, the next dose of atezolizumab/tiragolumab/RO7247669 may be administered. For subsequent infusions, consider administration of oral premedication with antihistamines, anti-pyretic medications, and/or analgesics and monitor closely for CRS. If symptoms do not resolve to Grade 1 or better for 3 consecutive days, contact the Medical Monitor.

Appendix 9: Guidelines for Management of Atezolizumab-, Tiragolumab-, and/or RO7247669-Specific Adverse Events

Table A9-7 Management Guidelines for Cytokine-Release Syndrome (cont.)

Event	Management

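### Appendix 9 gives two unreconciled conditions for the next dose after a steroid-treated Grade 2 cytokine-release syndrome: three days at Grade 1 or better (Table A9-7) and a steroid taper of at least one month (A9-2)

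*Combined protocol and SAP*

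**What the plan says.** The Grade 2 row of Table A9-7 (Appendix 9, section A9-12) makes steroids an option: "Consider IV corticosteroids (e.g., methylprednisolone 2 mg/kg/day or dexamethasone 10 mg every 6 hours". The same cell then sets the re-dosing condition: "If symptoms resolve to Grade 1 or better for 3 consecutive days, the next dose of atezolizumab/tiragolumab/RO7247669 may be administered". It says nothing about whether steroids were used or how far they have been reduced. The opening of Appendix 9 uses the label high-dose for "initiate treatment with high-dose corticosteroids (1–2 mg/kg/day prednisone or equivalent", so the methylprednisolone option falls in the range that the appendix itself calls high.

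Section A9-2 (Treatment Interruption) covers toxicity considered related to study treatment. Its trigger is "If corticosteroids are initiated for treatment of the toxicity", and the consequence is that "they must be tapered over ≥ 1 month to the equivalent of ≤ 10 mg/day oral prednisone before atezolizumab, tiragolumab, and/or RO7247669 can be resumed". The section adds, in the case of Cohort 1, that a later cycle is considered only if the benefit–risk profile is acceptable and "if the surgery can be conducted within 2 weeks of the planned date". If not: "Otherwise, subsequent treatment cycles should be omitted to allow the patient to proceed directly to surgery without further delay".

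On scope, the opening of Appendix 9 applies its resumption rules to atezolizumab, tiragolumab and RO7247669. The exceptions it lists all concern infusion-related reactions. The other tables that allow drug to resume after systemic steroids repeat the taper condition in a footnote. Table A9-7 has footnotes a to g, and none of them mentions a taper.

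**The concern.** After a Grade 2 CRS treated with steroids, a site that reads the CRS table finds a short condition based on symptoms. A site that reads A9-2 finds a mandatory taper lasting at least a month. No sentence makes one subject to the other.

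The timing matters most in Cohort 1, which has only two doses, 21 days apart, with surgery in Week 7. Which text a site follows decides whether Cycle 2 is given on schedule. That affects exposure within the experimental arms. It also affects the rate and duration of surgery delayed by treatment-related adverse events, which is a listed safety endpoint (Section 2, Table 2; Section 6.5). It leaves re-dosing after high-dose steroids without one clear rule.

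**Working it through.** The plan states no figure on this point, so there is none to reproduce. The check sets the two texts side by side and counts days.

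**Side by side, for a Grade 2 CRS treated with steroids**

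| | Table A9-7, Grade 2 | A9-2 |
|---|---|---|
| Force | Permission | Requirement |
| Condition | 3 consecutive days at Grade 1 or better | Taper over at least 1 month to 10 mg/day prednisone or less |
| Steroid use considered | No | Yes, it is the trigger |
| CRS exempted | Not stated | Not stated; the exception list covers infusion-related reactions only |

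**Inputs**
- Cycle length is 21 days (synopsis, study treatment table), so Cycle 2 falls on Day 1 + 21 = Day 22.
- Surgery is in Week 7 (Section 3.1.5), which is Day 6 × 7 + 1 = 43 to Day 49.
- A9-2 allows surgery up to 2 weeks (14 days) after the planned date.
- Assumption: 1 month is 28 to 31 days.
- Assumption: the 3-week gap from Cycle 2 to surgery is kept, and the planned surgery date is Day 43. The documents do not state that gap as a requirement.

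**Under Table A9-7.** For an event on Day 1 that resolves promptly, three days at Grade 1 or better are complete by about Day 4 to 5. Cycle 2 can go ahead on Day 22.

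**Under A9-2.** With the taper starting on day s and lasting m days, earliest resumption is s + m, the delay is s + m − 22, and surgery moves to Day 43 plus the delay.

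| Taper starts | m = 28 | m = 30 | m = 31 |
|---|---|---|---|
| Day 1 | Day 29, 7 days late, surgery Day 50 | Day 31, 9 days late, surgery Day 52 | Day 32, 10 days late, surgery Day 53 |
| Day 4 | Day 32, 10 days late, surgery Day 53 | Day 34, 12 days late, surgery Day 55 | Day 35, 13 days late, surgery Day 56 |

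**Can Cycle 2 be on time under A9-2?** That needs s ≤ 22 − m, which is −6, −8 and −9 for m = 28, 30 and 31. No taper can start before the first dose, so an on-time Cycle 2 is ruled out whenever steroids are used for a CRS at Cycle 1.

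**When is Cycle 2 omitted rather than delayed?** The delay stays within 14 days if s ≤ 36 − m, which is Day 8, 6 and 5 for m = 28, 30 and 31. A taper that starts later than this passes the limit. So does a longer one: 42 days from Day 1 ends on Day 43, a delay of 43 − 22 = 21 days, with surgery on Day 64 against a limit of 43 + 14 = Day 57.

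**Sensitivity to the planned surgery date.** If surgery was planned for Day 49, the limit is 49 + 14 = Day 63, and resumption by 63 − 21 = Day 42 still fits. The latest taper start becomes 42 − m: Day 14, 12 or 11. Omission becomes less likely, but Cycle 2 is still late.

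**The case against.** **A permission and a requirement do not contradict each other.** A site that waits for both conditions complies with both texts. This stands. A reader might infer that the two instructions cannot both be followed, and the wording does not support that. What remains is that the table never says its permission is subject to A9-2.

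**A9-2 may not be triggered.** Its taper sentence sits under treatment interruption and governs resumption. The Grade 2 CRS row interrupts the current infusion and speaks of the next dose; for an event on Day 1 no scheduled dose has been withheld. This reading is possible but is nowhere stated. Nor is the reading that the specific table overrides the general rule.

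**The missing footnote proves little.** Table A9-6 carries the taper footnote although both its rows discontinue drug permanently, so the footnote is partly boilerplate. Table A9-7 also has a different stated source, guidelines for CAR T-cell toxicities. Both points are fair. The footnote pattern is supporting evidence only; the case rests on A9-2 and the exception list.

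**These are guidelines.** Appendix 9 says that it informs rather than replaces clinical judgment, and the Medical Monitor can advise. That allows some variation between sites, but it does not tell a site which instruction the protocol intends, and A9-2 is worded as mandatory.

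**The text seen is incomplete.** It ends within Appendix 11, so Appendices 12 to 16 could not be checked for arm-specific wording. Section 5.3.5.1 does place the consolidated guidance on infusion-related reactions and CRS in Appendix 9.

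**Conclusion.** The inconsistency is real and narrow. It arises only when the optional steroids are given for a Grade 2 CRS, and only in the experimental arms, because adverse events in the control arm are managed under local prescribing information (A11-5.1.2.2). For a CRS at Cycle 1 in Cohort 1, Table A9-7 permits Cycle 2 on Day 22, while A9-2, read as applying, rules out an on-time dose. The difference is 7 to 10 days for a minimum-length taper starting on Day 1, taking a month as 28 to 31 days.

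Three stronger readings are tempting and not supported:
- **That the text used decides whether Cycle 2 is lost.** With an early, minimum-length taper it is delayed, and surgery stays inside the 2-week limit. Omission needs a later or longer taper, and depends on the assumed 3-week gap to surgery.
- **That a known number of patients is affected.** The documents give no rate of steroid-treated Grade 2 CRS, so no count can be derived.
- **That the pathologic response rate is biased by site.** Nothing in the documents allows an estimate. A patient who misses Cycle 2 still counts, because the efficacy-evaluable population needs only one dose of each assigned drug (Section 6). Any effect would come through exposure.

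The lost-cycle question is specific to Cohort 1. Cohort 2 has no surgery limit and currently no open arm.

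**What to change.** Reconcile three places in Appendix 9: the exception list in its opening, section A9-2, and the Grade 2 row of Table A9-7. State in that row whether the A9-2 taper condition applies when corticosteroids were given for CRS. If it does, a footnote like the one in the other tables is enough. If it does not, name CRS as an exception in A9-2 and in the opening list. The choice is a clinical one for the sponsor, and no view is taken here on which rule is right.

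The cost is one footnote or clause at the next amendment, with no extra patients, data or procedures.
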